10.4 ASSESSMENT OF AEs AND SAEs

Seriousness, causality, severity and expectedness will be assessed as though the participant is taking active IMP. Cases that are considered serious, possibly, probably or definitely related to IMP and unexpected (i.e. SUSARs) will be unblinded.

The Investigator is responsible for assessing each AE.

The Chief Investigator (CI) may not downgrade an event that has been assessed by an Investigator as an SAE or SUSAR, but can upgrade an AE to an SAE, SAR or SUSAR if appropriate.

10.4.1 Assessment Of Seriousness

The Investigator will make an assessment of seriousness as defined in Section 10.1.

10.4.2 Assessment Of Causality

Refer to Table B.

The assessment of relationship of adverse events to the administration of IMP is a clinical decision based on all available information at the time of the completion of the case report form. The categories described in Table B will be used to define the causality of the adverse event.

TABLE B: ASSESSMENT OF CAUSALITY						
The assessment of relationship of adverse events to the administration of IMP is a clinical decision. The following categories will be used to define the causality of the adverse event:						
Category	Definition					
Definitely:	There is clear evidence to suggest a causal relationship, and other possible contributing factors can be ruled out.					
Probably:	There is evidence to suggest a causal relationship, and the influence of other factors is unlikely					
Possibly	There is some evidence to suggest a causal relationship (e.g. the event occurred within a reasonable time after administration of the trial medication). However, the influence of other factors may have contributed to the event (e.g. the patient's clinical condition, other concomitant events).					
Unlikely	There is little evidence to suggest there is a causal relationship (e.g. the event did not occur within a reasonable time after administration of the trial medication). There is another reasonable explanation for the event (e.g. the patient's clinical condition, other concomitant treatments).					
Not related	There is no evidence of any causal relationship.					
Not Assessable	Unable to assess on information available.					

10.4.3 Assessment of Severity

The Investigator will make an assessment of severity for each AE/SAE and record this on the CRF or AE form according to one of the categories described in Table C:

TABLE C: ASSESSMENT OF SEVERITY OF AE/SAE						
The Investigator will make an assessment of severity for each AE/SAE and record this on the CRF or AE form according to one of the following categories:						
Category	Definition					
Mild	The adverse event does not interfere with the volunteer's daily routine, and does not require intervention; it causes slight discomfort					
Moderate	The adverse event interferes with some aspects of the volunteer's routine, or requires intervention, but is not damaging to health; it causes moderate discomfort					
Severe	The adverse event results in alteration, discomfort or disability which is clearly damaging to health					

Note: the term 'severe', used to describe the intensity, should not be confused with 'serious' which is a regulatory definition based on participant/event outcome or action criteria. For example, a headache may be severe but not serious, while a minor stroke is serious but may not be severe.

10.4.4 Assessment Of Expectedness

If an event is judged to be an AR/SAR, the evaluation of expectedness will be made based on knowledge of the reaction and the relevant product information documented in the SmPC refer to Table D.

TABLE D: ASSESSMENT OF EXPECTEDNESS OF AR/SAR				
Category	Definition			
Expected	An adverse event that is classed in nature as serious and which is consistent with the information about the IMP listed in the Investigator Brochure (or SmPC if Licensed IMP) or clearly defined in this protocol.			
Unexpected	An adverse event that is classed in nature as serious and which is not consistent with the information about the IMP listed in the Investigator Brochure (or SmPC if Licensed IMP)			

The reference document to be used to assess expectedness against the IMPs are:

Latest version of SmPC for fluoxetine and amiloride (both IMP supplied by Actavis) and riluzole (rilutek supplied by Sanofi) available from electronic medicines compendium: www.medicines.org.uk/

10.4.5 Seriousness

Seriousness as defined for an SAE in section 10.1

10.4.6 Non Reportable AEs/SAEs/SARs

The following will not be reported on the AE log in the CRF or to the sponsor as AEs/SAEs/SARs

10.4.6.1 Expected events related to SPMS:

SPMS is a progressive neurological condition and as such deterioration in neurological symptoms is expected. Therefore natural changes in motor, sensory, balance, sphincter (including urinary tract infections), visual, cognitive and fatigue levels are excluded as AEs/SAEs/SARs and will not be reported as such. In addition, relapses will not be counted as AEs/SAEs/SARs, but will be collated separately. They will be graded as follows (and see appendix 4):

Grade 1 relapse: relapse not treated with corticosteroids

Grade 2 relapse: relapse treated with corticosteroids, but not requiring hospitalisation Grade 3 relapse: relapse treated with corticosteroids and requiring in-patient hospitalisation; or relapse not treated with corticosteroids but requiring in-patient hospitalisation

If the participant feels they are experiencing a relapse, they should contact their local MS team (nurse/consultant) or General Practitioner as per routine practice, so that appropriate management can occur. They should also inform the MS-SMART team at their next scheduled visit, so that the relapse can be documented as per appendix 4. At the Investigator's/nurse's discretion the patient can attend for an unscheduled visit, see section 7.

If however, the investigators suspects that the disease has progressed faster due to the administration of the IMP, then they will report this as an unexpected adverse event (important medical event) to the sponsor.

All laboratory values will be recorded on the appropriate pages of the CRF. When there is a shift of a solitary, or group of values during the course of the study, which in the opinion of the Investigator may be classed as serious (life-threatening) and may or may not be deemed

> Sponsor No.12/0219 v7 Page **60** of **73**

attributable to the medication, this finding must be notified to the sponsor immediately. In these instances, the patient will be treated appropriately without regard to the confines of the protocol.

Full details of contraindications and side effects that have been reported following administration of the IMP can be found in the relevant Summary of Product Characteristics (SmPC).

Participants will be instructed to contact their Investigator at any time after consenting to join the trial if any symptoms develop. All adverse events (AE) that occur after joining the trial must be reported in detail in the Case Report Form (CRF) or AE form. In the case of an AE, the Investigator should initiate the appropriate treatment according to their medical judgement. Participants with AEs present at the last visit must be followed up until resolution of the event.

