Risk minimisation: patients with renal failure or hepatic failure are excluded from the trial. If clinically significant LFTs occur during the trial, the steps outlined in section 6.7.3 will be followed. FBC (including neutrophil count) is part of the safety blood panel, and the steps outlined in section 6.7.3 will take place if the neutrophil level falls below <1.0 $\times 10^9$ /l. The report of a febrile illness should prompt physicians to check white blood cell counts and to discontinue riluzole in case of neutropenia. If respiratory symptoms develop such as dry cough and/or dyspnoea, chest radiography should be performed, and in case of findings suggestive of interstitial lung disease (e.g. bilateral diffuse lung opacities), riluzole should be discontinued immediately. In the majority of the reported cases, symptoms resolved after drug discontinuation and symptomatic treatment.

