9.2.5 Interim analyses

Unblinded safety data will be monitored by a Data Monitoring Committee to ensure the ongoing safety of patients in the study. No formal interim analyses will be conducted.

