10 ADVERSE EVENTS

10.1 **DEFINITIONS**

Term	Definition
Adverse Event (AE)	Any untoward medical occurrence in a patient or clinical trial subject administered a medicinal product and which does not necessarily have a causal relationship with this treatment.
Adverse Reaction (AR)	Any untoward and unintended response in a subject to an investigational medicinal product which is related to any dose administered to that subject.

	This includes medication errors, uses outside of protocol (including misuse and abuse of product)
Serious adverse event (SAE), serious adverse reaction (SAR) or unexpected serious adverse reaction	 Any adverse event, adverse reaction or unexpected adverse reaction, respectively, that: results in death, is life-threatening, requires hospitalisation* or prolongation of existing hospitalisation, results in persistent or significant disability or incapacity, or consists of a congenital anomaly or birth defect
Important Medical Event	These events may jeopardise the subject or may require an intervention to prevent one of the above characteristics/consequences. Such events should also be considered 'serious'.
Unexpected adverse reaction	An adverse reaction the nature and severity of which is not consistent with the information about the medicinal product in question set out: (a) in the case of a product with a marketing authorization, in the summary of product characteristics for that product, (b) in the case of any other investigational medicinal product, in the
SUSAR	investigator's brochure relating to the trial in question. Suspected Unexpected Serious Adverse Reaction

*Expected events relating to SPMS resulting in hospitalisation including Grade 3 relapses will not meet the criteria of an SAE in this trial. See sections 10.4.6 and 10.4.6.1.

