10.5 REPORTING OF SAEs/SARs/SUSARs

Reporting to the sponsor will be completed as per UCL sponsor's SOP and using the UCL SAE forms (INV/S05).

All serious adverse events will be recorded in the hospital notes and the CRF, and the sponsor's AE log. The AE log will be reported to the sponsor at least once per year. All serious adverse events will need to be reported to the sponsor on a SAE form unless stated in section 10.4.6 whereby it lists expected SAEs that will not be reported to the sponsor, with justifications as to why they will not be reported. SAEs are reportable for 30 days after IMP administration – only SARs thereafter.

For reportable SAEs (those that are not described in section 10.4.6) the Chief/ Principal Investigator or delegated individual will complete the sponsor's serious adverse event form and the form will be faxed to the sponsor on [name], or preferably emailed to [contact] within 24 hours of his / her becoming aware of the event. A copy will be sent in tandem to the ECTU for notification. The Chief/ Principal Investigator or delegated individual will respond to any SAE queries raised by the sponsor as soon as possible.

All SUSARs must be notified to the sponsor immediately (or at least within 24 hours) according to the sponsor's written SOP.

The sponsor will notify the main REC and MHRA of all SUSARs. SUSARs that are fatal or lifethreatening must be notified to the MHRA and REC within 7 days after the sponsor has learned of them. Other SUSARs must be reported to the REC and MHRA within 15 days after the sponsor has learned of them.

The procedure for unblinding in the event of a SUSAR is described in section 5.5.2 of the protocol.

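### Section 10.4.6.1 excludes listed SPMS events, including urinary tract infections, even as SARs and with no seriousness limit, and conflicts with other recording and reporting rules in section 10

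*Protocol*

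**What the plan says.** Section 10.4.6 opens with "The following will not be reported on the AE log in the CRF or to the sponsor as AEs/SAEs/SARs". Section 10.4.6.1 then names natural changes in several SPMS domains and closes the list with "sphincter (including urinary tract infections), visual, cognitive and fatigue levels are excluded as AEs/SAEs/SARs and will not be reported as such". It attaches no seriousness criterion, and its only causal limit is the word natural.

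Three other places support the exclusion:
- The footnote to the hospitalisation criterion in section 10.1: "Expected events relating to SPMS resulting in hospitalisation including Grade 3 relapses will not meet the criteria of an SAE in this trial".
- Section 10.3, which leaves MS-related adverse events in the medical records and diary cards only.
- Section 10.5, which requires the SAE form "unless stated in section 10.4.6 whereby it lists expected SAEs that will not be reported to the sponsor".

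Section 10.4.6.1 has one causality carve-back. If the investigator suspects that the IMP made the disease progress faster, this goes to the sponsor as an unexpected adverse event (important medical event). Relapses are also outside AE reporting but are graded and collated separately.

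Other rules point the other way. The closing paragraph of section 10.4.6.1 requires every AE after joining the trial to be reported in the CRF or AE form. Section 10.5 says all SAEs are recorded in the hospital notes, the CRF and the sponsor's AE log. Sections 10.5 and 10.6 require SUSARs to be notified and state no exemption.

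**The concern.** Not reporting expected disease events one by one is a defensible choice in a progressive disease. The difficulty is how far this exclusion reaches. It names SARs, which are drug-related by definition. It names urinary tract infections outright. It does not separate a mild event from one that puts the patient in hospital or threatens life.

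Section 9.2.5 gives the safety oversight: "Unblinded safety data will be monitored by a Data Monitoring Committee to ensure the ongoing safety of patients in the study". The committee can compare arms only on what has been collected. A serious urinary infection that stays in site notes cannot be counted by arm, either during the trial or in the final safety tables. Sites also face instructions that they cannot all obey, so recording may differ between centres.

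**Working it through.** No figure in the plan bears on this point, so the check is a reading of the rules side by side.

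**1. Can an excluded event be a SAR?** Section 10.1 defines an adverse reaction as "Any untoward and unintended response in a subject to an investigational medicinal product which is related to any dose administered to that subject". A natural change of the disease is not a response to the drug. If the exclusion covers only natural changes, the word SARs has nothing to act on. If the word has effect, the exclusion covers drug-related events. The two cannot both stand.

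**2. Where does a listed event go if it leads to hospitalisation?**

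| Section | Rule | Result for the event |
|---|---|---|
| 10.1 footnote | Expected SPMS event with hospitalisation is not an SAE | No SAE status |
| 10.3 | MS-related events stay in source data | Off the CRF AE log and SAE form |
| 10.4.6 | Not on the CRF AE log, not to the sponsor | Off both |
| 10.4.6.1, closing paragraph | All AEs in the CRF or AE form | Recorded |
| 10.5, recording sentence | All SAEs in notes, CRF and sponsor's AE log | Recorded, if it is an SAE |
| 10.5, form sentence | SAE form waived for section 10.4.6 events | No form, yet the events are called SAEs |
| 10.5 and 10.6 | All SUSARs notified | Reported, if judged related and unexpected |

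The footnote and the form sentence disagree on whether these events are SAEs at all. The footnote also addresses hospitalisation only. A listed event that is life-threatening without hospitalisation remains an SAE under section 10.1 but is still excluded by section 10.4.6.

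**3. What if the drug is suspected?** The carve-back is worded for disease that progressed faster. It does not clearly cover an infection, or fatigue thought to be a drug reaction. The SUSAR duty is unqualified, but section 10.4.6.1 has already told the site that the event is expected and is not a SAR. Table D in section 10.4.4 also lets an event clearly defined in the protocol count as expected. A site could stop before it asks the SUSAR question.

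**4. Do the protocol's own drug profiles touch the listed domains?**
- Fatigue on riluzole: section 1.2.2.2 gives 15-20% against 12% on placebo in ALS, a difference of 15 − 12 = 3 to 20 − 12 = 8 percentage points.
- Fatigue on fluoxetine: section 1.2.2.1 reports minor increases over placebo and lists fatigue among the most common reactions.
- Infection: section 1.2.2.2 names neutropenia as a rare serious effect of riluzole and adds "The report of a febrile illness should prompt physicians to check white blood cell counts and to discontinue riluzole in case of neutropenia".

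So one listed item is a documented drug effect, and another could follow from one.

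**5. What is seen elsewhere?** Section 9.2.4 compares EDSS, walking, arm function, cognition, low-contrast vision, NFI fatigue and time to first relapse by arm. No outcome measure records urinary infection. For that event the AE log would be the only source of an arm comparison.

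**The case against.** The best defence is that the exclusion is limited to natural changes, under a heading about expected SPMS events, so an event attributed to the drug lies outside it. Several routes also remain open. Suspected IMP-driven progression reaches the sponsor as an important medical event, which section 10.1 treats as serious. SUSARs and all deaths (10.8) are reportable. Laboratory values go in the CRF, and life-threatening shifts are notified at once. Neutropenia itself would be seen in the full blood count at treatment visits and is covered in section 6.6.4. Relapses are graded, and most listed domains are outcome measures. The choice is declared and a reason is given.

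Most of this stands, and it sets the limit of the point. A reader might infer that drug-related events in these domains never reach the sponsor, the SUSAR route or any arm comparison, and that only deaths remain reportable. The routes just listed rule that out. A reader might also want to put a size on the loss by assuming infection rates. The documents give no such rate and link none of the three drugs directly to urinary infection, so any figure would be invented.

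The defence does not explain why SARs are named, why urinary infection is listed with no seriousness limit, or how a site should choose between section 10.3 or 10.4.6 and the contrary sentences in 10.4.6.1 and 10.5.

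**Conclusion.** The concern holds in a limited form and should be fixed. The SAR exclusion contradicts the definition in section 10.1, it has no seriousness limit, and its carve-back reaches only accelerated progression. It also conflicts with the closing paragraph of 10.4.6.1, the recording sentence of 10.5 and the SUSAR duty in 10.5 and 10.6. What can be lost is mainly serious urinary infection, together with other serious or suspected-related listed events that none of the remaining routes catches.

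The size cannot be given from the documents. The primary analysis of brain volume change is untouched; the effect is on the completeness of the safety comparison. The conclusion assumes that sites apply section 10.4.6 as written. The Data Monitoring Committee charter and the sponsor's reporting SOP are not at hand, and either might add a route that the protocol does not mention.

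**What to change.** - Delete SARs from the exclusion in section 10.4.6 and its heading.
- State that any listed event judged possibly, probably or definitely related to the IMP follows the normal AR, SAR and SUSAR route, whether or not it represents faster progression.
- Record any listed event that meets a section 10.1 seriousness criterion on the CRF log, and give the Data Monitoring Committee the counts by arm. The waiver of the 24-hour sponsor form can stay for events that are expected and unrelated.
- Reconcile the section 10.1 footnote, 10.3, 10.4.6, the closing paragraph of 10.4.6.1, 10.5 and 10.6, so that each listed event has one recording rule and one reporting rule.

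The cost is protocol wording and a few extra CRF log entries. Section 1.2.2.1 says that recruitment is complete, so entries for events that have already happened would be made from source records, where section 10.2 requires all AEs to be kept.

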10.5 REPORTING OF SAEs/SARs/SUSARs

Reporting to the sponsor will be completed as per UCL sponsor's SOP and using the UCL SAE forms (INV/S05).

All serious adverse events will be recorded in the hospital notes and the CRF, and the sponsor's AE log. The AE log will be reported to the sponsor at least once per year. All serious adverse events will need to be reported to the sponsor on a SAE form unless stated in section 10.4.6 whereby it lists expected SAEs that will not be reported to the sponsor, with justifications as to why they will not be reported. SAEs are reportable for 30 days after IMP administration – only SARs thereafter.

For reportable SAEs (those that are not described in section 10.4.6) the Chief/ Principal Investigator or delegated individual will complete the sponsor's serious adverse event form and the form will be faxed to the sponsor on [name], or preferably emailed to [contact] within 24 hours of his / her becoming aware of the event. A copy will be sent in tandem to the ECTU for notification. The Chief/ Principal Investigator or delegated individual will respond to any SAE queries raised by the sponsor as soon as possible.

All SUSARs must be notified to the sponsor immediately (or at least within 24 hours) according to the sponsor's written SOP.

The sponsor will notify the main REC and MHRA of all SUSARs. SUSARs that are fatal or lifethreatening must be notified to the MHRA and REC within 7 days after the sponsor has learned of them. Other SUSARs must be reported to the REC and MHRA within 15 days after the sponsor has learned of them.

The procedure for unblinding in the event of a SUSAR is described in section 5.5.2 of the protocol.

10.6 FOLLOW UP PROCEDURES

After initially recording an AE or recording and reporting an SAE, the Investigator will follow each participant until resolution or death of the participant. Follow up information on an SAE will be reported to the JRO office.

AEs still present in participants at the last study visit or reported in 30 day follow up period after completion of trial medication will be monitored until resolution of the event, or until no longer medically indicated.

Any SUSAR related to the IMP will need to be reported to the sponsor irrespective of how long after IMP administration the reaction has occurred.

10.7 DEVELOPMENT SAFETY UPDATE REPORTS

The sponsor will provide the main REC and the MHRA with Development Safety Update Reports (DSUR) which will be written in conjunction with the trial team and the sponsor's office. The report

will be submitted within 60 days of the Developmental International Birth Date (DIBD) of the trial each year until the trial is declared ended. This will be done in accordance with the sponsor's SOP (SPON/S17).

10.8 NOTIFICATION OF DEATH

All deaths will be reportable to the Sponsor. This report will be immediate.

10.9 OVERDOSE

Sites will record details of reported overdoses on the deviation log and inform the trial manager at ECTU as soon as possible after being made aware of the information. Sources of information can include patient-reported, pill counts, diary cards and drug charts. ECTU will notify the sponsor that an overdose has occurred.

In the event that an SAE is associated with the overdose the SAE reporting procedure in addition should be followed (section 10). Details of the overdose will documented in the SAE form.

An overdose is defined as taking double the normal medication/day for 1 day or more. If an overdose has taken place, the patient will suspend medication for at least 48 hours, and resume the previous dose as soon as possible afterwards, at the discretion of the PI. The patient will continue in trial.

The individual IMP data is given below. It is clear that if clinically significant symptoms occur, the trial participant should be unblinded to aid medical management.

Amiloride: no data are available; it is not known whether the drug is dialysable. No specific antidote is available. The most likely signs and symptoms are dehydration and electrolyte imbalance which should be treated by established methods. Therapy should be discontinued and the patient closely observed. Emesis should be induced or gastric lavage performed if ingestion is recent. Treatment is symptomatic and supportive. If hyperkalaemia occurs, active measures should be taken to reduce plasma potassium levels.

Riluzole: Neurological and psychiatric symptoms, acute toxic encephalopathy with stupor, coma, and methemoglobinemia have been observed in isolated cases. In case of overdose, treatment is symptomatic and supportive.

Fluoxetine: Cases of overdose of fluoxetine alone usually have a mild course. Symptoms of overdose have included nausea, vomiting, seizures, cardiovascular dysfunction ranging from asymptomatic arrhythmias to cardiac arrest (including very rare cases of Torsades de Pointes), pulmonary dysfunction, and signs of altered CNS status ranging from excitation to coma. Fatality attributed to overdose of fluoxetine alone has been extremely rare. Cardiac and vital signs monitoring are recommended, along with general symptomatic and supportive measures. No specific antidote is known.

Forced diuresis, dialysis, haemoperfusion, and exchange transfusion are unlikely to be of benefit. Activated charcoal, which may be used with sorbitol, may be as or more effective than emesis or lavage. In managing overdosage, consider the possibility of multiple drug involvement. An extended time for close medical observation may be needed in patients who have taken excessive quantities of a tricyclic antidepressant if they are also taking, or have recently taken, fluoxetine.

11. **PREGNANCY**

Pregnancy is not considered an AE or SAE; however, the Investigator will collect pregnancy information for any female participants or female partners of male participants who become pregnant while participating in the study.

Reporting to the sponsor will be completed as per the sponsor's SOP and using the UCL pregnancy notification forms (INV/S05). The Investigator will record the information on the sponsors Pregnancy Notification Form and fax this to the sponsor on [name] or preferably emailed to [contact], within 24 hours of being made aware of the pregnancy.

All pregnant female participants and partners of male participants will be followed up until following the outcome of the pregnancy.

